5.7 Criteria for Taking a Participant Off Study

Participants will be removed from study when any of the following criteria apply:

- Lost to follow-up
- Withdrawal of consent for data submission
- Death

The reason for taking a participant off study, and the date the participant was removed, must be documented in the case report form (CRF). In addition, the study team will ensure Off Treatment/Off Study information is updated in OnCore in accordance with DF/HCC policy REGIST-101.

6 DOSING DELAYS/DOSE MODIFICATIONS

6.1 Dosing/Delays/Omission/Modification

- The descriptions and grading scales found in the revised NCI Common Terminology Criteria for Adverse Events (CTCAE) version 5.0 will be utilized for dose delays and dose modifications.
- If multiple adverse events are seen, administer dose based on the greatest reduction required for any single adverse event observed. Reductions apply to treatment given in the preceding cycle and are based on adverse events observed since the prior dose.
- If more than one of these apply, use the most stringent (i.e. the greatest dose reduction).
- Dosing interruptions are permitted in the case of medical / surgical events or logistical reasons not related to study therapy (e.g., elective surgery, unrelated medical events, patient vacation, and/or holidays). Participants held for these reasons require prior approval from the PI and should resume therapy within 6 weeks of the scheduled interruption. The reason for interruption should be documented in the participant's study record.

- If treatment is withheld > 8 weeks from the last dose of cabozantinib or nivolumab, the patient should discontinue study therapy.
- For management of AEs which can be clearly attributed to cabozantinib or nivolumab, independent dose modification for either agent is allowed as described. For AEs without clear attribution to either study treatment, management of toxicity should include dose modifications or delay of both agents.
- Participants who require dose delay should be re-evaluated weekly or more frequently if clinically indicated and resume dosing when re-treatment criteria are met.
- Delayed doses of nivolumab and cabozantinib should be administered as soon as the participant meets criteria to resume treatment. If a dose has been delayed, the participant should not wait until the next scheduled dosing date.
- Dosing interruptions will not impact assessments or cycle/day scheduling.
- Restarting of treatment after dose interruption must be discussed with the PI.
- In order to standardize the management of adverse events, treatment management algorithms recommended for utilization in this study are included in Appendix B.

6.2 Dose Levels

Dose Level	Nivolumab (IV)	Cabozantinib (tablet dose expression)
0 (starting dose)	240 mg	40mg daily
-1	-	20mg daily

Dose reductions are permitted for cabozantinib but not for nivolumab.

6.3 Hematologic Toxicities

For **grade 3 neutropenia with documented infection, grade 3 neutropenia ≥ 5 days, or grade 4 neutropenia**, delay cabozantinib and nivolumab until toxicity resolves to grade ≤ 1 , then resume cabozantinib with one dose level reduction and nivolumab without dose reduction.

For **grade 3 febrile neutropenia**, delay cabozantinib and nivolumab until ANC grade ≤ 1 and temperature to $\leq 38.0^{\circ}\text{C}$, then resume cabozantinib with one dose level reduction and nivolumab without dose reduction.

For **grade 4 febrile neutropenia**, discontinue cabozantinib. Resume nivolumab when ANC grade ≤ 1 .

For **grade 3 thrombocytopenia with clinically significant bleeding or grade 4 thrombocytopenia**, continue nivolumab but delay cabozantinib until platelet count $\geq 100,000/\text{mm}^3$, then resume cabozantinib with one dose level reduction.

For **grade 4 anemia**, continue nivolumab but delay cabozantinib and use supportive care (e.g. red blood cell transfusions) as clinically indicated according to institutional guidelines until toxicity resolves to grade ≤ 1 , then resume cabozantinib with one dose level reduction.

6.4 Diarrhea/Colitis

Participants experiencing intolerable Grade 2 diarrhea or Grade 3 diarrhea unable to be managed with standard antidiarrheal treatments should consult a gastrointestinal (GI) doctor for potential endoscopy and biopsy to help distinguish between cabozantinib vs. nivolumab mediated toxicity.

If a biopsy is performed and:

- there is T cell infiltration indicative of nivolumab-induced colitis, nivolumab should be held and managed with corticosteroids. Once diarrhea returns to Grade 1, restart cabozantinib and nivolumab as indicated in the management table below.
- there is no T cell infiltration indicative of nivolumab-induced colitis, when diarrhea returns to Grade 1 nivolumab should be resumed at the same dose at the discretion of the investigator. Cabozantinib should also be resumed at a reduced dose.

Treatment may be restarted following the resolution of colitis. In addition, if the patient is being managed with corticosteroids, treatment should not be restarted until the steroids have been tapered down to a prednisone dose <10 mg/day. Patients who resume treatment should be monitored closely for signs of renewed diarrhea.

Table: Management of Diarrhea/Colitis

Grade	Management
Grade 1	
Continue nivolumab and cabozantinib.Start Anti-diarrheal agent (e.g., Imodium) – up to 3 agents are permittedClose monitoring.
Grade 2	
Hold nivolumab and cabozantinibAdminister anti-diarrheal agent (e.g., Imodium).If symptoms persist > 5 days or recur, initiate therapy with Prednisone 60 mg/day or equivalentIf improved to Grade ≤ 1 within 8 weeks:
Taper steroids over ≥ 1 monthRestart Nivolumab when corticosteroids have been reduced to the equivalent of prednisone ≤ 10 mg/day.Restart Cabozantinib at a reduced dose when corticosteroids have been reduced to the equivalent of prednisone ≤ 10 mg/day.
Grade 3	
Hold nivolumab and cabozantinib.
 
Treat with IV steroids (1-2 mg/kg/day methylprednisolone or equivalent) and convert to oral steroids (prednisone 60 mg/day or

	
equivalent) after improvement
 
 • If improved to Grade ≤ 1 within 8 weeks: 
 ○ Taper steroids over ≥ 1 month ○ Restart Nivolumab when corticosteroids have been reduced to the equivalent of prednisone ≤ 10 mg/day. ○ Restart Cabozantinib at a reduced dose when corticosteroids have been reduced to the equivalent of prednisone ≤ 10 mg/day.
Grade 4	
 • Permanently discontinue nivolumab and hold cabozantinib. • Treat with IV steroids (1–2 mg/kg/day methylprednisolone or equivalent) and convert to oral steroids (prednisone 60 mg/day or equivalent) after improvement • When symptoms improve to Grade ≤ 1, taper steroids over ≥ 1 month • If symptoms are not improving after 48 hours of initiating steroids or are worsening, addition of an alternative immunosuppressive agent (e.g., mycophenolate or TNF-α antagonist) may be considered. • If the subject was unequivocally deriving clinical benefit, the subject may be able to resume cabozantinib at reduced dose as determined by the investigator.

6.5 Hepatobiliary Disorders

It is recommended that participants with elevation of ALT, AST, and/or bilirubin have more frequent laboratory monitoring of these parameters. If possible, hepatotoxic concomitant medications should be discontinued in participants who develop increased values of ALT, AST, or bilirubin.

Guidelines in the following table should be used for dose modifications.

Transaminase elevation CTCAE v. 5.0	Intervention
\leq Grade 1 AST or ALT $>$ ULN to $3.0 \times$ ULN and/or Total bilirubin $>$ ULN – $1.5 \times$ ULN	Continue study treatment, monitor liver function tests (LFTs) weekly for at least 4 weeks
Grade 2 AST or ALT $>$ 3.0 to $</= 5.0 \times$ ULN and/or Total bilirubin $>$ ULN – $1.5 \times$ ULN to $</= 3 \times$ ULN	Hold cabozantinib and nivolumab Monitor LFTs at least twice weekly until return to baseline or Grade $</= 1$ Consider referral to a hepatologist If persistent $>$ 5 days, start prednisone 60 mg/day or equivalent. When LFTs resolve to baseline or Grade ≤ 1 and steroid dose is

Transaminase elevation CTCAE v. 5.0	Intervention
	
prednisone \leq 10 mg/day or equivalent, restart nivolumab and cabozantinib at a reduced dose.
 
* Permanently discontinue protocol therapy for conditions fulfilling Hy's law with elevations $>3 \times$ ULN of ALT or AST concurrent with $>2 \times$ ULN total bilirubin without other explanation


Grade 3 AST or ALT > 5.0 to $\leq 20.0 \times$ ULN and/or Total bilirubin $>$ ULN – $3.0 \times$ ULN to $\leq 10.0 \times$ ULN
	
Hold cabozantinib and nivolumab. Monitor LFTs every 48–72 hours until LFTs return to baseline or Grade ≤ 1 Consider referral to hepatologist and liver biopsy to establish etiology of hepatic injury Start prednisone 60 mg/day or equivalent With first occurrence:
 
 If LFTs do not resolve to Grade < 3 within 7 days, permanently discontinue nivolumab and continue holding cabozantinib. When LFTs resolve to baseline or Grade ≤ 1, taper steroids over ≥ 1 month. When steroid dose is prednisone \leq 10 mg/day or equivalent, restart Nivolumab and Cabozantinib at a reduced dose. Subjects receiving cabozantinib at a daily dose of 20 mg may be restarted at the same dose if deemed safe at the discretion of the principal investigator. 
If recurs: permanently discontinue nivolumab. If the subject was unequivocally deriving clinical benefit, the subject may be able to resume cabozantinib at reduced dose as determined by the investigator.
 
* Permanently discontinue protocol therapy for conditions fulfilling Hy's law with elevations $>3 \times$ ULN of ALT or AST concurrent with $>2 \times$ ULN total bilirubin without other explanation

Grade 4 AST or ALT $> 20.0 \times$ ULN and/or Total bilirubin $>$ ULN $10.0 \times$ ULN
	
Permanently discontinue nivolumab and hold cabozantinib and inform the principle investigator.
 
Obtain hepatology consult and liver biopsy to establish etiology of hepatic injury.
 
Start prednisone 60 mg/day or equivalent.
 
If LFT results do not decrease within 48 hours after initiation of systemic steroids, consider addition of an alternative immunosuppressive agent (e.g., mycophenolate) to the corticosteroid regimen.
 
If LFTs resolve to baseline or Grade ≤ 1, taper steroids over ≥ 1 month.

Transaminase elevation CTCAE v. 5.0	Intervention
	If the subject was unequivocally deriving clinical benefit, the subject may be able to resume cabozantinib at reduced dose as determined by the investigator.

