6.23 Creatinine Levels/ Renal Insufficiencies

Table: Management of Creatinine Levels/Renal Insufficiencies

Grade	Management
≤ 1	Continue protocol therapy. Monitor weekly until return to baseline.
2-3 (>1.5 baseline to $\leq 6.3.0 \times$ ULN)	Hold nivolumab and cabozantinib until \leq Grade 1. Monitor creatinine every 2-3 days. Start 0.5 to 1.0 mg/Kg/day methylprednisolone IV or oral equivalent. Consider consulting nephrology and obtaining a renal biopsy.
4 ($>6.0 \times$ ULN)	Discontinue nivolumab and hold cabozantinib. Monitor creatinine daily. Start 1.0 – 2.0 mg/Kg/day methylprednisolone IV or oral equivalent. Consult nephrologist and consider obtaining a renal biopsy.

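### The bilirubin limits in the Section 6.5 dose-modification table are misprinted, so low values meet two or three rows with different actions; separately, one creatinine limit in Section 6.23 is unreadable

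*Combined protocol and SAP*

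**What the plan says.** Section 6.5 directs sites to its table for dose modifications. The bilirubin entries and the actions beside them are:

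- Grade 1 or below: "Total bilirubin $>$ ULN – $1.5 \times$ ULN". Action: "Continue study treatment, monitor liver function tests (LFTs) weekly for at least 4 weeks".
- Grade 2: "Total bilirubin $>$ ULN – $1.5 \times$ ULN to $</= 3 \times$ ULN". Action: hold both drugs; "If persistent $>$ 5 days, start prednisone 60 mg/day or equivalent".
- Grade 3: "Total bilirubin $>$ ULN – $3.0 \times$ ULN to $\leq 10.0 \times$ ULN". Action: hold both drugs and start prednisone without waiting. On first occurrence, "If LFTs do not resolve to Grade < 3 within 7 days, permanently discontinue nivolumab and continue holding cabozantinib".
- Grade 4: "Total bilirubin $>$ ULN $10.0 \times$ ULN". Action: stop nivolumab permanently and hold cabozantinib.

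The AST/ALT limits in the same four rows run from ULN to 3.0, 3.0 to 5.0, 5.0 to 20.0, and above 20.0 x ULN.

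Three other places bear on this. Section 5.2.2 allows later cycles at bilirubin up to 1.5 x ULN (2.0 x ULN with documented Gilbert's syndrome). Section 6.1 names CTCAE v5.0 as the scale for dose delays and modifications, and tells sites to take the most stringent option when several apply. Section 6.23 gives the middle creatinine row as "2-3 (>1.5 baseline to $\leq 6.3.0 \times$ ULN", with Grade 4 above 6.0 x ULN.

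**The concern.** These limits select the action. If one bilirubin value satisfies several rows, two sites can follow the printed table and treat the same patient differently. One continues both drugs; another holds both, and may start a steroid and the 7-day clock for stopping nivolumab. The 7-day rule and the restart conditions are themselves written in grades, so the overlap carries into them.

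The trial enrols at most 35 patients and provides for external sites. Raised ALT/AST and hepatitis are listed in Section 7.1 as expected or observed events, so the table is likely to be used. Inconsistent holds would show up in exposure and steroid use.

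**Working it through.** The plan states no computed figure on this point. The check is whether each laboratory value falls in exactly one row.

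**Notation.** In the Grade 1 row the dash after ULN can only mean a range from ULN to 1.5 x ULN. The Grade 2 row repeats that expression and adds an upper limit of 3. The Grade 3 row opens the same way, with 3.0 and then an upper limit of 10.0. Grades 2 and 3 therefore each carry two candidate lower limits: ULN and 1.5 x ULN for Grade 2, ULN and 3.0 x ULN for Grade 3.

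**Rule.** A value x, in multiples of ULN, meets a row if lower < x ≤ upper. As printed, the bands are Grade 1 (1, 1.5], Grade 2 (1, 3] and Grade 3 (1, 10]. Treating the Grade 1 upper limit as inclusive is an assumption. Grade 4 is taken first as x > 10, then literally as x > 1. The last column drops the leading ULN, giving (1, 1.5], (1.5, 3], (3, 10] and > 10.

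| Bilirubin (x ULN) | Rows met as printed, Grade 4 as > 10 | Rows met as printed, Grade 4 as > ULN | Rows met with leading ULN dropped |
|---|---|---|---|
| 1.2 | 1, 2, 3 | 1, 2, 3, 4 | 1 |
| 1.5 | 1, 2, 3 | 1, 2, 3, 4 | 1 |
| 2.0 | 2, 3 | 2, 3, 4 | 2 |
| 3.0 | 2, 3 | 2, 3, 4 | 2 |
| 5.0 | 3 | 3, 4 | 3 |
| 12 | 4 | 4 | 4 |

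For x = 1.2: 1 < 1.2 ≤ 1.5, 1 < 1.2 ≤ 3 and 1 < 1.2 ≤ 10 all hold, hence three rows. The same test on AST/ALT at 2, 4, 10 and 25 x ULN gives one row each (Grades 1, 2, 3 and 4).

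**Against Section 5.2.2.** At 1.2 x ULN a patient may start a cycle (1.2 ≤ 1.5). As printed, the Grade 2 and Grade 3 rows of 6.5 both hold treatment at that value.

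**Against Section 6.1.** Applied to holds and steroids, the most-stringent rule sends 1.2 x ULN to the Grade 3 action and leaves the Grade 1 bilirubin entry with no effect. The rule defines stringency by size of dose reduction. On that measure it does not separate Grades 2 and 3, since both rows provide for a restart at a reduced dose. Either way, the conflict with 5.2.2 remains.

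**Creatinine, Section 6.23.** The upper limit 6.3.0 has three plausible readings. Baseline is taken as equal to ULN, an assumption.

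- As 6.0: it meets Grade 4 (> 6.0) with no gap and no overlap.
- As 6.3: values above 6.0 and up to 6.3 x ULN meet two rows.
- As 3.0: values above 3.0 and up to 6.0 x ULN meet no row.

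**The case against.** The strongest reply is that the intent is recoverable. The second numbers chain without a gap (1.5, then 1.5 to 3, then 3.0 to 10.0, then 10.0), the AST/ALT limits beside them are contiguous, the column is headed with CTCAE v5.0, and 5.2.2 agrees with continuing up to 1.5 x ULN. A consistently literal reading would also put 1.2 x ULN in Grade 4, which nobody would intend. This stands as far as it goes: it is a drafting error, and an experienced reader would probably resolve it correctly. It does not remove the need for correction, because sites are told to use the table and should not have to infer the limits that trigger a hold.

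Text extraction might be blamed. For bilirubin that is unlikely, since the pattern recurs across rows while the adjacent AST/ALT text is intact. For the creatinine limit, which occurs once, it cannot be excluded.

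A reader might infer two stronger things. One is that 6.23 double-grades patients. Only one of the three readings gives any overlap, and then over a narrow band. Grades 2 and 3 share one row and one action, and the Grade 4 limit is legible. What is shown is an unreadable limit. The other is that the safety endpoint is affected. Sections 16.3 and 16.5 grade adverse events and laboratory values by CTCAE v5.0, not by these table limits, so tabulated grades do not depend on the misprint.

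**Conclusion.** The bilirubin point holds. As printed, and with Grade 4 read as above 10 x ULN, every value above ULN and up to 3 x ULN meets more than one row: three rows up to 1.5 x ULN, two rows above that. The rows carry different hold and steroid actions, and those at the low end contradict 5.2.2. The Grade 4 entry is malformed as well. The size rests on the dash having the same meaning in every row; if the leading ULN is a stray insertion, the overlap disappears. The text does not say which reading applies.

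The creatinine limit in 6.23 is unreadable as printed, and no more than that is claimed.

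The reach is limited to dose holds, steroid use and exposure. The response rate, sample size and error rates are untouched. The separate rule in 6.5 for combined transaminase and bilirubin elevation has its own limits and does not depend on these bands. Nothing in the documents shows that any patient was managed wrongly because of the misprint.

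**What to change.** Restate all four bilirubin rows in 6.5, each with one unambiguous lower limit and, where it applies, one upper limit, so that they join without overlap as the AST/ALT limits do. Reconcile them with 5.2.2 and with the CTCAE v5.0 scale named in 6.1. The 5.2.2 allowance for Gilbert's syndrome has no counterpart in the 6.5 table and belongs in the same reconciliation.

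In 6.23, check the Grade 2-3 upper limit against the source file. If the misprint is there, replace it with one readable limit that is consistent with the Grade 4 limit.

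The choice of limits and actions is the sponsor's, and none is proposed here. The cost is a correction to the affected table entries in the next amendment, with notice to sites. No procedure, visit or analysis changes.

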3.1.6 ECOG performance status ≤ 1 (Karnofsky $\geq 60\%$, see Appendix A)

3.1.7 Participants must have normal organ and marrow function as defined below:

- absolute neutrophil count	$\geq 1,500/\text{mcL}$
- platelets	$\geq 100,000/\text{mcL}$
- total bilirubin	$\leq 1.5 \times$ institutional upper limit of normal (ULN) (or $2.0 \times$ ULN in patients with documented Gilbert's Syndrome)
- AST (SGOT)/ALT (SGPT)	$\leq 2.5 \times$ ULN or $\leq 3 \times$ ULN for participants with documented liver metastases
- creatinine	$< 1.5 \times$ ULN
Or	
creatinine clearance	$\geq 40 \text{ mL/min}$ (using Cockcroft-Gault formula) for participants with creatinine levels above institutional normal
- Urine protein/creatinine ratio (UPCR)	≤ 1
- PT/INR or partial thromboplastin time (PTT) test	$< 1.3 \times$ the laboratory ULN within 7 days before the first dose of study treatment.

3.1.8 Negative urine pregnancy test for women of childbearing potential.

3.1.9 Participant must be able to swallow pills.

3.1.10 The participant is capable of understanding and complying with the protocol and has signed the informed consent document.

3.2

Exclusion Criteria

- 3.2.1 Major surgery (eg, GI surgery, removal or biopsy of brain metastasis) within 8 weeks before first dose of study treatment. Complete wound healing from major surgery must have occurred 1 month before first dose and from minor surgery (eg, simple excision, tooth extraction) at least 10 days before first dose. Subjects with clinically relevant ongoing complications from prior surgery are not eligible.
- 3.2.2 Participants who are receiving any other investigational agents.
- 3.2.3 Participants who have received a prior cabozantinib.
- 3.2.4 Participants who have received prior therapy with an anti-PD-1, anti-PD-L1, anti- PD-L2, anti-CD137, or anti-Cytotoxic T-lymphocyte-associated antigen-4 (CTLA-4) antibody (including nivolumab, pembrolizumab, ipilimumab, and any other antibody or drug specifically targeting T-cell co-stimulation or checkpoint pathways)
- 3.2.5 Participants with known Central Nervous System(CNS) metastases should be excluded from this clinical trial because of their poor prognosis and because they often develop progressive neurologic dysfunction that would confound the evaluation of neurologic and other adverse events.
- 3.2.6 The participant has tumor in contact with, invading, or encasing major blood vessels or radiographic evidence of significant cavitary pulmonary lesions.

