5.2.2 Subsequent Cycles

- absolute neutrophil count $\geq 1,000/\text{mcL}$
- total bilirubin $\leq 1.5 \times$ institutional upper limit of normal (ULN) (or $2.0 \times$ ULN in patients with documented Gilbert's Syndrome)
- AST(SGOT)/ALT(SGPT) $\leq 2.5 \times$ institutional ULN or $\leq 3 \times$ institutional ULN for participants with documented liver metastases
- Urine pregnancy test in women of child-bearing age every 4 weeks (+/- 1 week)

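### Section 6.5 has no Gilbert's exception, so bilirubin that section 5.2.2 accepts at cycle start falls in the Grade 2 hold row (minor)

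*Combined protocol and SAP*

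**What the plan says.** Three places in the protocol set the bilirubin limit at 1.5 × ULN and raise it to 2.0 × ULN for Gilbert's syndrome. Eligibility (3.1.7) has the higher limit for "ULN in patients with documented Gilbert's Syndrome"; the Cycle 1 Day 1 criteria (5.2.1) repeat it; and the criteria for later cycles (5.2.2) again allow it "in patients with documented Gilbert's Syndrome".

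The section 6.5 table sorts patients by multiples of ULN only, and none of its four rows mentions Gilbert's syndrome. In the Grade ≤1 row, with bilirubin up to 1.5 × ULN, the instruction is "Continue study treatment, monitor liver function tests (LFTs) weekly for at least 4 weeks". In the Grade 2 row it is "Hold cabozantinib and nivolumab Monitor LFTs at least twice weekly until return to baseline or Grade" 1 or lower. If the abnormality persists beyond "5 days, start prednisone 60 mg/day or equivalent". Once the tests have resolved to baseline or Grade ≤1 and the steroid dose is down to prednisone 10 mg/day "or equivalent, restart nivolumab and cabozantinib at a reduced dose". Section 6.2 does not permit nivolumab reductions, so the reduction applies to cabozantinib, whose only level below 40 mg is 20 mg.

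The table's one allowance for an alternative cause, "ULN total bilirubin without other explanation", belongs to the Hy's law stopping rule printed in the Grade 2 and Grade 3 rows.

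**The concern.** The plan chose to treat patients with Gilbert's syndrome and gave them a higher bilirubin limit, both to enter and to start each cycle. The table that governs treatment between those points does not carry that limit over. The study calendar draws chemistry, including total bilirubin, on Day 1 and Day 15, so a single Day 1 result can satisfy 5.2.2 and at the same time call for a hold under 6.5.

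At stake is individual treatment. A patient the plan meant to keep on therapy could have both drugs interrupted, receive high-dose prednisone, and come back on half the cabozantinib dose. The steroid step also sits badly with section 5.4.1, which says systemic glucocorticoids should be avoided except for radiation symptoms or events of suspected immune cause.

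**Working it through.** The plan states no figure on this point, so the check compares thresholds.

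**Inputs.** Gilbert's limit 2.0 × ULN and general limit 1.5 × ULN (3.1.7, 5.2.1, 5.2.2). Grade ≤1 upper bound 1.5 × ULN and Grade 2 upper bound 3 × ULN (6.5). Bilirubin and AST/ALT are joined by and/or in 6.5, so bilirubin alone is sufficient. Cabozantinib levels 40 mg and 20 mg (6.2).

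**The Grade 2 bilirubin cell.** It is printed with two lower bounds, ULN and 1.5 × ULN. The Grade 3 cell shows the same pattern (ULN and 3.0 × ULN). Taking the first bound literally would make the rows overlap, so I read Grade 2 as >1.5 to ≤3 × ULN. The conclusion does not depend on this: with a lower bound of either 1.0 or 1.5 × ULN, the band >1.5 to 2.0 × ULN lies inside the row.

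**Side by side, for documented Gilbert's syndrome with AST/ALT no higher than Grade 1:**

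| Bilirubin (× ULN) | Entry (3.1.7, 5.2.1) | Cycle start (5.2.2) | Table (6.5) |
|---|---|---|---|
| >1.0 to 1.5 | accepted | accepted | Grade ≤1: continue |
| >1.5 to 2.0 | accepted | accepted | Grade 2: hold both drugs |
| >2.0 to 3.0 | not accepted | not accepted | Grade 2: hold both drugs |

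Only the middle line conflicts. Its width is 2.0 − 1.5 = 0.5 × ULN. Example: at 1.8 × ULN the patient passes 5.2.2 (1.8 ≤ 2.0) and meets the Grade 2 row (1.5 < 1.8 ≤ 3.0). Patients without Gilbert's syndrome are capped at 1.5 × ULN everywhere, so no conflict arises for them.

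**What the row then does depends on baseline.**
- *Baseline already in the band.* The value that puts the patient in the row is also the resolution end point. The hold should be short and prednisone is hard to justify, but the restart instruction still says reduced cabozantinib.
- *Baseline ≤1.5 × ULN, rising into the band on treatment.* The hold applies, prednisone starts if the rise lasts more than 5 days, and the row's restart condition is a return to ≤1.5 × ULN, although 5.2.2 would accept up to 2.0.

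**Dose consequence.** 20/40 = 50% of the starting dose.

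**The case against.** The best defence is that section 6 manages adverse events, not constitutional values. Section 6.1 ties reductions to events seen since the last dose, and 6.5 opens with patients whose liver values become raised. A Gilbert's patient at a usual 1.8 × ULN has had no new event. The baseline wording protects such patients further. Appendix B, recommended by 6.1, says to continue immuno-oncology therapy when the cause is non-inflammatory. A footnote in 6.26 limits dose adjustment to toxicity related, or of unclear relation, to cabozantinib. Section 6.5 calls its table guidelines, and 6.1 requires restarts to be discussed with the PI. For a patient who newly rises into the band, holding two drugs with known liver toxicity is a defensible choice. Finally, 3.1.7 and 5.2.1 act before there is any dose to hold, so only 5.2.2 operates alongside 6.5.

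Much of this stands as mitigation, and an attentive investigator would often reach the sensible answer. It does not remove the gap. Entry to the Grade 2 row is by multiple of ULN with no baseline or Gilbert's exception. The Appendix B note does not cover cabozantinib. The 6.26 footnote belongs to a table for toxicities not already described. PI discussion comes after the hold. Where several dose modifications apply, 6.1 favours the most stringent, which points towards the reduction.

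Two stronger readings are tempting and are not supported.
- A reader might infer that a patient who stays at 1.8 × ULN must lose therapy under the 8-week limit in 6.1. That section does not name the re-treatment criteria it means. If 5.2.2 is meant, 1.8 × ULN passes, and the outcome also assumes no PI judgement along the way.
- A reader might see a second conflict in AST/ALT, because 5.2.2 stops at 2.5 × ULN without liver metastases while 6.5 continues to 3.0. Both rules can be followed together: the next cycle waits, with no steroid and no dose cut.

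**Conclusion.** The inconsistency is real and minor. For documented Gilbert's syndrome, an isolated bilirubin above 1.5 and up to 2.0 × ULN is acceptable at cycle start under 5.2.2 and calls for a hold of both drugs under 6.5, with a cabozantinib reduction to follow. Patients whose baseline is already in that band are partly protected.

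The whole of the extra Gilbert's allowance lies in the hold row, but that describes only the overlap of two ranges. It does not mean that the allowance has no effect in practice, and it measures no loss of dose or response. The documents do not say how many Gilbert's patients are expected among the up to 35 participants; that the number is small is my judgement. The objective response analysis, the sample size and the error rates do not change.

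The conclusion rests on the table being applied as written and on bilirubin alone being enough to enter a row. It does not rest on how the misprinted Grade 2 cell is read.

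**What to change.** Add one sentence to the 6.5 table: *In documented Gilbert's syndrome with AST/ALT in the Grade ≤1 range, the continue row and the bilirubin restart limit extend to 2.0 × ULN; Grade 2 bilirubin management starts above 2.0 × ULN.* Reprint the Grade 2 bilirubin range as >1.5 to ≤3 × ULN.

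The AST/ALT condition confines the exception to isolated bilirubin elevation. The Hy's law stop needs bilirubin above 2 × ULN together with ALT or AST above 3 × ULN, so it is unchanged. A narrower exception tied only to each patient's baseline would protect those who enter in the band, but would leave 5.2.2 and 6.5 in conflict for those who rise into it.

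The cost is a wording amendment with no added tests or visits; it can go with the next amendment through the approvals in section 14. The small downside is that a new isolated rise within 1.5 to 2.0 × ULN in a Gilbert's patient would be monitored weekly and not held.
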